10.2.1. Footnotes for Schedule of Events (Phase 2)

1. Every effort should be made to perform all screening and baseline activities on the same day. Randomization within the IRT system and administration of study drug should occur on the same day (day 1). All samples will be collected before study drug administration at baseline visit except post-infusion PK samples.
2. For a given day, the visit may occur in clinic, as a home-based visit (defined as visits by home health care staff, at mobile units, and/or testing centers), or by phone. All samples will be collected as indicated whether the patient is hospitalized or has been discharged.
3. Patients must provide separate consent to collect blood samples as part of the optional PGx sub-study. Blood sample for RNA must be collected pre-dose on day 1. Blood sample for DNA should be collected at the screening/baseline visit but may be collected at any visit.
4. Refer to protocol Section 9.2.1.2 for diagnostic test requirements during screening.
5. Pregnancy testing will be performed locally in women of childbearing potential (WOCBP) only. Negative pregnancy test must be confirmed prior to study drug administration. Serum or urine pregnancy test are both acceptable. Refer to protocol Section 9.2.3.4 for more information on pregnancy testing and contraceptive measures.
6. Medical history should include collecting onset of pneumonia symptoms.
7. Clinical and oxygen status will be collected 3 times during the screening/baseline visit period: prior to randomization, just prior to dosing, and post-dose. Clinical and oxygen status will be collected and recorded in the eCRF as described in protocol Section 9.2.5.2.
8. Vital signs (including temperature, blood pressure, heart rate, and SpO₂) will be collected pre-dose and post-dose, as described in protocol Section 9.2.3.1.
9. Only treatment-emergent SAEs and AESIs will be recorded in the eCRF.
10. Patients discharged from the hospital may receive phone follow-up for treatment-emergent SAEs, treatment-emergent AESIs, and/or targeted concomitant medications as indicated in protocol Table 2 (post-discharge phone follow-up). These visits may occur in addition to any in-person visit listed for the given day. Phone visits will have a window of ± 1 day.
11. Medications will be reviewed and recorded. Only the targeted medications listed in protocol Section 9.2.3.3 will be recorded in the eCRF.
12. Hematology, blood chemistry, and coagulation tests will be collected at the visits indicated and results will be entered in the eCRF. Hematology, blood chemistry, and coagulation tests must be collected prior to dosing. Testing will be performed locally, and standard-of-care labs are acceptable.
13. Actual dosing time and PK sample collection times will be recorded.
14. At the baseline visit, blood samples for PK assessment will be taken predose and within 60 minutes after the end of infusion (EOI). The EOI sample should be collected from the arm contralateral to that used for IV infusion. If not medically feasible, the EOI sample can be drawn from the same arm, but not from the infusion catheter.

15. The window for predose ADA sample collection is as close to administration of study drug as is reasonable. Actual dosing times and ADA sample collection times will be recorded.

10.3. Criteria for Potentially Clinically Significant Values (PCSV)

Parameter	PCSV	Comments
Clinical Chemistry		
ALT*	>3 and \leq 5 ULN and baseline \leq 3 ULN* >5 and \leq 10 ULN and baseline \leq 5 ULN >10 and \leq 20 ULN and baseline \leq 10 ULN >20 ULN and baseline \leq 20 ULN	Enzymes activities must be expressed in ULN, not in IU/L. Concept paper on DILI – FDA draft Guidance Oct 2007. Each category is calculated independently. * At least one level is required; multiple levels are optional for phase 2/3 studies. If it is desirable to get the distribution across the different PCSV levels, additional shift table on \leq 3, >3 to \leq 5, > 5 to \leq 10, >10 to \leq 20, and > 20 category for baseline vs. post baseline may be provided
AST*	>3 and \leq 5 ULN and baseline \leq 3 ULN* >5 and \leq 10 ULN and baseline \leq 5 ULN >10 and \leq 20 ULN and baseline \leq 10 ULN >20 ULN and baseline \leq 20 ULN	Enzymes activities must be expressed in ULN, not in IU/L. Concept paper on DILI – FDA draft Guidance Oct 2007. Each category is calculated independently. * At least one level is required, multiple levels are optional for phase 2/3 studies. If it is desirable to get the distribution across the different PCSV levels, additional shift table on \leq 3, >3 to \leq 5, > 5 to \leq 10, >10 to \leq 20, and > 20 category for baseline vs. post baseline may be provided
Alkaline Phosphatase	>1.5 ULN and baseline \leq 1.5 ULN	Enzyme activity must be expressed in ULN, not in IU/L. Concept paper on DILI – FDA draft Guidance Oct 2007.

Parameter	PCSV	Comments
Total Bilirubin*	>1.5 and \leq 2 ULN and baseline \leq 1.5 ULN* >2 ULN and baseline \leq 2.0 ULN	Must be expressed in ULN, not in $\mu\text{mol}/\text{L}$ or mg/L . Categories are cumulative. Concept paper on DILI – FDA draft Guidance Oct 2007. * At least one level is required, multiple levels are optional for phase 2/3 studies. If it is desirable to get the distribution of significant level, additional shift table on ≤ 1.5 , > 1.5 to ≤ 2.0 and > 2.0 category for baseline vs. post baseline may be provided
Conjugated Bilirubin	>35% Total Bilirubin and TBILI>1.5 ULN, and baseline Total Bilirubin \leq 35% or TBILI \leq 1.5 ULN	Conjugated bilirubin determined on a case-by-case basis.
ALT and Total Bilirubin	ALT>3 ULN and TBILI>2 ULN, and baseline ALT \leq 3 ULN or TBILI \leq 2ULN	Concept paper on DILI – FDA draft Guidance Oct 2007.
CPK*	>3 and \leq 10 ULN and baseline \leq 3ULN* >10 ULN and baseline \leq 10ULN	FDA Feb 2005. Am J Cardiol April 2006. Categories are cumulative. * At least one level is required, multiple levels are optional for phase 2/3 studies. If it is desirable to get the distribution of significant level, additional shift table on ≤ 3 , > 3 to ≤ 10 , and > 10 category for baseline vs. post baseline may be provided
Creatinine	$\geq 150 \mu\text{mol}/\text{L}$ (Adults) or $\geq \text{ULN}$ (if $\text{ULN} \geq 150 \mu\text{mol}/\text{L}$) and baseline $< 150 \mu\text{mol}/\text{L}$ or $< \text{ULN}$ (if $\text{ULN} \geq 150 \mu\text{mol}/\text{L}$) $\geq 30\%$ change from baseline $\geq 100\%$ change from baseline	Benichou C., 1994. 3 independent criteria

Parameter	PCSV	Comments
Creatinine Clearance (Cockcroft's formula)	<15 ml/min and baseline \geq 15 ml/min (end stage renal impairment) \geq 15 - <30 ml/min and baseline \geq 30 ml/min (severe renal impairment) \geq 30 - < 60 ml/min and baseline \geq 60 ml/min (moderate renal impairment) \geq 60 - < 90 ml/min and baseline \geq 90 ml/min (mild renal impairment)	Use is optional. FDA draft guidance 2010 Four independent criteria, will provide additional shift table if needed
Uric Acid		
Hyperuricemia:	$>408 \mu\text{mol/L}$ or $>\text{ULN}$ (if $\text{ULN} \geq 408 \mu\text{mol/L}$) and baseline $\leq 408 \mu\text{mol/L}$ or $\leq \text{ULN}$ (if $\text{ULN} \geq 408 \mu\text{mol/L}$)	Harrison- Principles of Internal Medicine 17 th Ed., 2008. Two independent criteria
Hypouricemia:	$<120 \mu\text{mol/L}$ or $<\text{LLN}$ (if $\text{LLN} \leq 120 \mu\text{mol/L}$) and baseline $\geq 120 \mu\text{mol/L}$ or $\geq \text{LLN}$ (if $\text{LLN} \leq 120 \mu\text{mol/L}$)	
Blood Urea Nitrogen	$\geq 17 \text{ mmol/L}$ or $\geq \text{ULN}$ (if $\text{ULN} \geq 17 \text{ mmol/L}$) and baseline $< 17 \text{ mmol/L}$ or $< \text{ULN}$ (if $\text{ULN} \geq 17 \text{ mmol/L}$)	Two independent criteria
Chloride		
Hypochloremia:	$<80 \text{ mmol/L}$ or $<\text{LLN}$ (if $\text{LLN} \leq 80 \text{ mmol/L}$) and baseline $\geq 80 \text{ mmol/L}$ or $\geq \text{LLN}$ (if $\text{LLN} \leq 80 \text{ mmol/L}$) $>115 \text{ mmol/L}$ or $>\text{ULN}$ (if $\text{ULN} \geq 115 \text{ mmol/L}$) and baseline $\leq 115 \text{ mmol/L}$ or $\leq \text{ULN}$ (if $\text{ULN} \geq 115 \text{ mmol/L}$)	Two independent criteria
Hyperchloremia:		
Sodium		
Hyponatremia:	$\leq 129 \text{ mmol/L}$ or $\leq \text{LLN}$ (if $\text{LLN} \leq 129 \text{ mmol/L}$) and baseline $> 129 \text{ mmol/L}$ or $> \text{LLN}$ (if $\text{LLN} \leq 129 \text{ mmol/L}$) $\geq 160 \text{ mmol/L}$ or $\geq \text{ULN}$ (if $\text{ULN} \geq 160 \text{ mmol/L}$) and baseline $< 160 \text{ mmol/L}$ or $< \text{ULN}$ (if $\text{ULN} \geq 160 \text{ mmol/L}$)	Two independent criteria
Hypernatremia:		

Parameter	PCSV	Comments
Potassium	<3 mmol/L or <LLN (if LLN≤3 mmol/L) and baseline ≥ 3 mmol/L or ≥LLN (if LLN≤3 mmol/L)	FDA Feb 2005.
Hypokalemia	≥5.5 mmol/L or ≥ULN (if ULN≥5.5 mmol/L) and baseline <5.5 mmol/L or <ULN (if ULN≥5.5 mmol/L)	Two independent criteria
Hyperkalemia		
Total Cholesterol	≥7.74 mmol/L or ≥ULN (if ULN≥7.74 mmol/L) and baseline < 7.74 mmol/L or <ULN (if ULN≥7.74 mmol/L)	Threshold for therapeutic intervention.
Triglycerides	≥4.6 mmol/L or ≥ULN (if ULN≥4.6 mmol/L) and baseline < 4.6 mmol/L or <ULN (if ULN≥4.6 mmol/L)	Threshold for therapeutic intervention.
Lipasemia	≥3 ULN and baseline < 3 ULN	
Amylasemia	≥3 ULN and baseline < 3 ULN	
Glucose		
Hypoglycaemia	≤3.9 mmol/L and <LLN and baseline >3.9 mmol/L or ≥ LLN ≥11.1 mmol/L (unfasted); ≥7 mmol/L (fasted) and baseline < 11.1 mmol/L (unfasted); <7 mmol/L (fasted)	ADA Jan 2008.
Hyperglycaemia		
HbA1c	>8% and baseline ≤ 8%	
Albumin	≤25 g/L or ≤LLN (if LLN≤25 g/L) and baseline >25 g/L or >LLN (if LLN≤25 g/L)	
CRP	>2 ULN or >10 mg/L (if ULN not provided) and baseline ≤2 ULN or ≤10 mg/L (if ULN not provided)	FDA Sept 2005.
Hematology		

Parameter	PCSV	Comments
WBC	$<3.0 \text{ Giga/L}$ or $<\text{LLN}$ (if $\text{LLN} \leq 3.0 \text{ Giga/L}$) and baseline $\geq 3.0 \text{ Giga/L}$ or $\geq \text{LLN}$ (if $\text{LLN} \leq 3.0 \text{ Giga/L}$) (Non-Black); $<2.0 \text{ Giga/L}$ or $<\text{LLN}$ (if $\text{LLN} \leq 2.0 \text{ Giga/L}$) and baseline $\geq 2.0 \text{ Giga/L}$ or $\geq \text{LLN}$ (if $\text{LLN} \leq 2.0 \text{ Giga/L}$) (Black)* $\geq 16.0 \text{ Giga/L}$ or $\geq \text{ULN}$ (if $\text{ULN} \geq 16.0 \text{ Giga/L}$) and baseline $< 16 \text{ Giga/L}$ or $<\text{ULN}$ (if $\text{ULN} \geq 16.0 \text{ Giga/L}$)	Increase in WBC: not relevant. *The default criteria. Summary by race (black and Non-black) are optional. To be interpreted only if no differential count available.
Lymphocytes	$>4.0 \text{ Giga/L}$ or $>\text{ULN}$ (if $\text{ULN} \geq 4.0 \text{ Giga/L}$) and baseline $\leq 4.0 \text{ Giga/L}$ or $\leq \text{ULN}$ (if $\text{ULN} \geq 4.0 \text{ Giga/L}$)	
Neutrophils	$<1.5 \text{ Giga/L}$ or $<\text{LLN}$ (if $\text{LLN} \leq 1.5 \text{ Giga/L}$) for Non-Black or $<1.0 \text{ Giga/L}$ or $<\text{LLN}$ (if $\text{LLN} \leq 1.0 \text{ Giga/L}$) for Black and baseline $\geq 1.5 \text{ Giga/L}$ or $\geq \text{LLN}$ (if $\text{LLN} \leq 1.5 \text{ Giga/L}$) for Non-Black or $\geq 1.0 \text{ Giga/L}$ or $\geq \text{LLN}$ (if $\text{LLN} \leq 1.0 \text{ Giga/L}$) for Black* $<1.5 \text{ Giga/L}$ or $<\text{LLN}$ (if $\text{LLN} \leq 1.5 \text{ Giga/L}$) and baseline $\geq 1.5 \text{ Giga/L}$ or $\geq \text{LLN}$ (if $\text{LLN} \leq 1.5 \text{ Giga/L}$) (Non-Black); $<1.0 \text{ Giga/L}$ or $<\text{LLN}$ (if $\text{LLN} \leq 1.0 \text{ Giga/L}$) and baseline $\geq 1.0 \text{ Giga/L}$ or $\geq \text{LLN}$ (if $\text{LLN} \leq 1.0 \text{ Giga/L}$) (Black) $<0.5 \text{ Giga/L}$ regardless of baseline value or race	International Consensus meeting on drug-induced blood cytopenias, 1991. *The default criteria. By race (black and Non-black) are optional.
Monocytes	$>0.7 \text{ Giga/L}$ or $>\text{ULN}$ (if $\text{ULN} \geq 0.7 \text{ Giga/L}$) and baseline $\leq 0.7 \text{ Giga/L}$ or $\leq \text{ULN}$ (if $\text{ULN} \geq 0.7 \text{ Giga/L}$)	
Basophils	$>0.1 \text{ Giga/L}$ or $>\text{ULN}$ (if $\text{ULN} \geq 0.1 \text{ Giga/L}$) and baseline $\leq 0.1 \text{ Giga/L}$ or $\leq \text{ULN}$ (if $\text{ULN} \geq 0.1 \text{ Giga/L}$)	
Eosinophils	$>0.5 \text{ Giga/L}$ or $>\text{ULN}$ (if $\text{ULN} \geq 0.5 \text{ Giga/L}$) and baseline $\leq 0.5 \text{ Giga/L}$ or $\leq \text{ULN}$ (if $\text{ULN} \geq 0.5 \text{ Giga/L}$)	Harrison- Principles of Internal Medicine 17 th Ed., 2008.

Parameter	PCSV	Comments
Hemoglobin	
≤ 115 g/L or \leq LLN (if LLN≤ 115 g/L) for male or ≤ 95 g/L or \leq LLN (if LLN≤ 95 g/L) for female and baseline > 115 g/L or $>$ LLN (if LLN≤ 115 g/L) for male or > 95 g/L or $>$ LLN (if LLN≤ 95 g/L) for Female*
 
≤ 115 g/L or \leq LLN (if LLN≤ 115 g/L) and baseline > 115 g/L or $>$ LLN (if LLN≤ 115 g/L) for male;
 
≤ 95 g/L or \leq LLN (if LLN≤ 95 g/L) and baseline > 95 g/L or $>$ LLN (if LLN≤ 95 g/L) for Female.
 
≥ 185 g/L or \geq ULN (if ULN≥ 185 g/L) for male or ≥ 165 g/L or \geq ULN (if ULN≥ 165 g/L) for female and baseline < 185 g/L or $<$ ULN (if ULN≥ 185 g/L) for male or < 165 g/L or $<$ ULN (if ULN≥ 165 g/L) for Female*
 
≥ 185 g/L or \geq ULN (if ULN≥ 185 g/L) and baseline < 185 g/L or $<$ ULN (if ULN≥ 185 g/L) for Male;
 
≥ 165 g/L or \geq ULN (if ULN≥ 165 g/L) and baseline < 165 g/L or $<$ ULN (if ULN≥ 165 g/L) for Female
 
Decrease from Baseline ≥ 20 g/L
	
Three criteria are independent.
 
*The default criteria. By gender (male and female) are optional.
 
Criteria based upon decrease from baseline are more relevant than based on absolute value. Other categories for decrease from baseline can be used (≥ 30 g/L, ≥ 40 g/L, ≥ 50 g/L).

Parameter	PCSV	Comments
Hematocrit	
≤ 0.37 v/v or \leqLLN (if LLN≤ 0.37 v/v) for Male or ≤ 0.32 v/v or \leqLLN (if LLN≤ 0.32 v/v) for Female and baseline > 0.37 v/v or $>$LLN (if LLN≤ 0.37 v/v) for Male or > 0.32 v/v or $>$LLN (if LLN≤ 0.32 v/v) for Female*
 
≤ 0.37 v/v or \leqLLN (if LLN≤ 0.37 v/v) and baseline > 0.37 v/v or $>$LLN (if LLN≤ 0.37 v/v) for Male ; ≤ 0.32 v/v or \leqLLN (if LLN≤ 0.32 v/v) and baseline > 0.32 v/v or $>$LLN (if LLN≤ 0.32 v/v) for Female
 
≥ 0.55 v/v or \geqULN (if ULN≥ 0.55 v/v) for Male or ≥ 0.5 v/v or \geqULN (if ULN≥ 0.5 v/v) for Female and baseline < 0.55 v/v or $<$ULN (if ULN≥ 0.55 v/v) for Male < 0.5 v/v or $<$ULN (if ULN≥ 0.5 v/v) for Female*
 
≥ 0.55 v/v or \geqULN (if ULN≥ 0.55 v/v) and baseline < 0.55 v/v or $<$ULN (if ULN≥ 0.55 v/v) for Male ; ≥ 0.5 v/v or \geqULN (if ULN≥ 0.5 v/v) and baseline < 0.5 v/v or $<$ULN (if ULN≥ 0.5 v/v) for Female
	
Two Criteria are independent
 
*The default criteria. By gender (male and female) are optional.

RBC	≥ 6 Tera/L or \geq ULN (if ULN ≥ 6 Tera/L) and baseline < 6 Tera/L or $<$ ULN (if ULN ≥ 6 Tera/L)	Unless specifically required for particular drug development, the analysis is redundant with that of Hb.
Platelets	
< 100 Giga/L or $<$LLN (if LLN≤ 100 Giga/L) and baseline ≥ 100 Giga/L or \geqLLN (if LLN≤ 100 Giga/L)
 
≥ 700 Giga/L or \geqULN (if ULN≥ 700 Giga/L) and baseline < 700 Giga/L or $<$ULN (if ULN≥ 700 Giga/L)
	
International Consensus meeting on drug-induced blood cytopenias, 1991.
 
Two independent criteria

Coagulation Parameters		
INR	> 2.5	

Parameter	PCSV	Comments
PT	>2.5 x ULN	
aPTT	>2.5 x ULN	
Vital signs		
HR	<45 bpm and decrease from baseline \geq 20 bpm \geq 120 bpm and increase from baseline \geq 20 bpm	To be applied for all positions except STANDING
SBP	\leq 95 mmHg and decrease from baseline \geq 20mmHg \geq 160 mmHg and increase from baseline \geq 20 mmHg	To be applied for all positions except STANDING
DBP	\leq 45 mmHg and decrease from baseline \geq 10 mmHg \geq 110 mmHg and increase from baseline \geq 10 mmHg	To be applied for all positions except STANDING

Signature Page for VV-RIM-00160102 v1.0

ESig Approval

2021 23:17:35 GMT+0000

ESig Approval

00

ESig Approval

21 23:47:28 GMT+0000

ESig Approval

00

ESig Approval

00

ESig Approval

2021 00:44:30 GMT+0000

Signature Page for VV-RIM-00160102 v1.0 Approved

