4.6.3. Laboratory Safety Variables

Blood Chemistry

Samples for laboratory testing will be collected at visits according to the schedule of events in Section [10.2](#).

Tests will include:

Sodium	Blood urea nitrogen (BUN)	Alkaline phosphatase
Potassium	Aspartate aminotransferase (AST)	Creatinine
Chloride	Alanine aminotransferase (ALT)	Creatine phosphokinase (CPK)
Carbon dioxide	Total bilirubin	Lactate dehydrogenase (LDH)
Glucose	Albumin	C-reactive protein (CRP)
Ferritin		

Hematology

Hematology, urinalysis, and pregnancy testing samples will be analyzed by the local laboratory.

Tests will include:

Hemoglobin	Differential:
Hematocrit	Neutrophils
Red blood cells (RBCs)	Lymphocytes
White blood cells (WBCs)	Monocytes
Platelet count	Basophils
	Eosinophils

Other Laboratory Tests

Coagulation tests: D-dimer, prothrombin time (PT/INR), activated partial thromboplastin time (aPTT).

Laboratory results, vital signs, and other diagnostic results or findings that are appraised by the investigator and determined by investigator to fulfil the criteria of TEAEs (grade 3 or 4), treatment-emergent SAEs, or treatment-emergent AESIs will be reported.

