5.7.2. Clinical Laboratory Measurements

Laboratory test results will be summarized by baseline and change from baseline to each scheduled assessment time with descriptive statistics.

A treatment-emergent Potential Clinically Significant abnormal value (PCSV) is a laboratory value that was normal at Screening and Baseline but abnormal after treatment with study drug. See Appendix [10.3](#) for the criteria of PCSV values.

Number and percentage of patients with a potentially clinically significant value (PCSV) at any post-randomization time point will be summarized for each clinical laboratory test for all patients and separately for patients in whom the PCSV criterion was normal or missing at baseline.

Shift tables based on baseline normal/abnormal and other tabular and graphical methods may be used to present the results for laboratory tests of interest.

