Medical history ⁶	X																										
Weight and height	X																										
Randomization		X																									
Treatment																											
Study drug administration			X																								
Efficacy Assessments (Virologic)																											
NP swab for SARS-CoV-2 RT-qPCR		X				X		X	X	X	X	X	X	X	X	X	X	X	X	X	X	X	X	X	X		
Efficacy Assessments (Clinical/Oxygen Status)																											
Oxygen delivery device status ⁷		X ⁷	X ⁷		X		X	X	X	X	X	X	X	X	X	X	X	X	X	X	X	X	X	X	X		
Vital status ⁷		X ⁷	X ⁷		X		X	X	X	X	X	X	X	X	X	X	X	X	X	X	X	X	X	X	X		
Hospitalization status ⁷		X ⁷	X ⁷		X		X	X	X	X	X	X	X	X	X	X	X	X	X	X	X	X	X	X	X		
Safety Assessments																											
Vital signs ⁸			X		X																						
Treatment-emergent grade ≥2 infusion-related reactions ^{9,10}					← Continuous monitoring →																						
Treatment-emergent grade ≥2 hypersensitivity reactions ^{9,10}																											
Treatment-emergent SAEs ^{9,10}																											

Day	Screening/Baseline ¹				Hospitalization/Post-Discharge Period ²																Follow-up Period		EOS					
	-1 to 1				Discharge Before Day 29	2	3	4	5	6	7	8	9	10	11	12	13	14	15	16, 17, 18, 19, 20, 21	22	23, 24, 25, 26, 27, 28	29	36	43	50	57	
	Screen	Pre-Dose	Dose	Post-Dose																								
Week Number	1				1	1	1	1	1	1	1	2	2	2	2	2	2	2	3	3	4	4	5	6	7	8	9	
Visit Number	1				2	3	4	5	6	7	8	9	10	11	12	13	14	15	16-21	22	23-28	29	30	31	32	33		
Window (Days)					±1						±1	±1	±1	±1	±1	±1	±1	±1	±3		±3	±3	±3	±3	±3	±3		
Targeted concomitant medications ^{10,11}	X	X			← Continuous monitoring →																							
Post-discharge phone follow-up ¹⁰																									X	X	X	X
Pregnancy follow-up																												X
Local Laboratory Testing																												
Hematology (including differential) ¹²	X																											X
Blood chemistry (including AST, ALT, CRP, ferritin, LDH) ¹²	X																											X
Coagulation tests (D-dimer, PT/INR, aPTT) ¹²	X																											X
Pharmacokinetics/Immunogenicity																												
Serum for PK ¹³			X ¹⁴		X ¹⁴	X																					X	
Serum for ADA ¹⁵			X ¹⁵			X																						X
Pharmacodynamic/Biomarkers																												
Serum for serology		X																										X
Serum for cytokines and CK-MB		X																										X
Serum for research and cardiac biomarkers			X																									X

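### The SAP's only combined transaminase-and-bilirubin criterion uses ALT alone, so a combined case that rests on AST is never counted as one

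*SAP*

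**What the plan says.** SAP 10.3 gives ALT and AST the same four bands, starting above 3 ULN, with the same source comment and the same instruction: "Each category is calculated independently". Total bilirubin has its own row, whose upper level begins ">2 ULN and baseline". Two further liver rows combine two conditions:

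- The conjugated bilirubin row begins ">35% Total Bilirubin and TBILI>1.5 ULN". It sets one bilirubin measure against another and contains no transaminase.
- The row headed ALT and Total Bilirubin requires "ALT>3 ULN and TBILI>2 ULN", provided that at baseline ALT was at or below 3 ULN or total bilirubin at or below 2 ULN.

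AST is routinely available. SAP 4.6.3 includes "Aspartate aminotransferase (AST)" in the chemistry panel with ALT, total bilirubin and CPK. The schedules of events in the SAP appendix list "Blood chemistry (including AST, ALT, CRP, ferritin, LDH)" as one draw.

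For reporting, SAP 5.7.2 says that the number and percentage of patients with a PCSV "at any post-randomization time point will be summarized for each clinical laboratory test". Shift tables and other displays are optional there. Protocol 11.4.10.2 carries the same commitments and adds no joint AST-bilirubin display.

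**The concern.** A row that pairs a transaminase with bilirubin exists to show patients in whom both rose, which the single-test rows cannot do. The SAP treats ALT and AST alike when each stands alone, then uses only ALT when bilirubin is added. It gives no reason for the difference.

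At stake is a reported safety count. If the SAP is followed to the letter, a patient whose combined abnormality rests on AST is left out of the one table line meant for combined abnormalities. Adverse-event collection is targeted in phases 2 and 3: footnote 9 to the phase 2/3 schedule limits recording to treatment-emergent SAEs and AESIs. The laboratory displays therefore carry more of the safety description than they would with full adverse-event collection, and it is worth having the combined line complete.

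A smaller point concerns the same row. It does not say whether the two values must come from one sample.

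**Working it through.** No sample size, power or alpha figure is involved, so the check applies the written rules to a defined patient.

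**Step 1: inputs.** From SAP 10.3, take the AST row, the total bilirubin row and the ALT and Total Bilirubin row. The patient has, after baseline, AST above 3 ULN, total bilirubin above 2 ULN and ALT at or below 3 ULN. At baseline, AST was at or below 3 ULN and total bilirubin at or below 2 ULN.

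**Step 2: apply each row.**

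| Row in SAP 10.3 | Condition that decides | Result |
|---|---|---|
| ALT | ALT above 3 ULN | Not met |
| AST | AST above 3 ULN, in the band it falls in | Met |
| Total bilirubin | above 2 ULN, baseline at or below 2 ULN | Met |
| ALT and Total Bilirubin | ALT above 3 ULN and bilirubin above 2 ULN | Not met, because of ALT |
| Conjugated bilirubin | two bilirubin measures | Contains no transaminase; conjugated bilirubin is not in the SAP 4.6.3 panel |

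The patient is counted under AST and under bilirubin, and nowhere as a combined case. With the transaminase condition read as ALT or AST, the patient would be counted.

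The AST entry is itself conditional. The comment in SAP 10.3 requires at least one AST level to be reported and makes several levels optional in phase 2/3 studies. Whether the patient appears in the AST row therefore depends on which bands are shown.

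**Step 3: can the joint count be recovered from the separate counts?** Let N be the number of patients, *a* the number above the AST limit and *b* the number above the bilirubin limit. The number above both lies anywhere from max(0, *a* + *b* − N) to min(*a*, *b*). When *a* and *b* are small relative to N, the lower limit is 0, so the two margins are compatible with no joint case and with as many as min(*a*, *b*). The ALT-based joint count does not close the gap:

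(ALT or AST) joint count = ALT joint count + number with AST above 3 ULN, bilirubin above 2 ULN and ALT at or below 3 ULN

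The last term is not produced by any display the SAP commits to.

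**Step 4: look for a commitment elsewhere.** SAP 5.7.2 and protocol 11.4.10.2 summarise PCSVs test by test. The optional displays in 5.7.2 could include a joint plot or table, but none is specified.

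**Step 5: timing.** The combined row does not mention the sample. Laboratory summaries in phases 2/3 are windowed to days 7, 15 and 29 (SAP 6.4, Table 11). One programmer could require both values from one draw. Another could pair ALT from day 7 with bilirubin from day 29, which are 29 − 7 = 22 days apart. The text settles neither reading.

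**The case against.** The strongest reply is that nothing in the documents requires AST in the combined row. The row cites an external guidance paper, which is not part of the documents. Equal thresholds in the single-test rows do not oblige the SAP to treat the two enzymes as interchangeable in a joint rule. ALT alone may be a deliberate choice of specificity, since AST also rises with muscle injury. This stands in part: the row is not an internal contradiction, and it should not be called an error against the plan's own text. It does not answer the narrower point that the wider count is missing and cannot be rebuilt from what is shown.

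A second reply is that liver injury is not a flagged risk. Protocol 3.3.2 names hypersensitivity and infusion reactions, immunogenicity and embryo-fetal toxicity, and the AESIs in SAP 4.6.2 are infusion-related and hypersensitivity reactions. That is correct, and it keeps the point small.

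Two stronger readings are tempting, and the documents do not support them:

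- A reader might infer that a non-serious liver event could be seen only through these laboratory criteria. Protocol 9.2.4 requires significantly abnormal results to be repeated and, if unresolved or unexplained, taken to the Medical/Study Director. Protocol 10.1.1 requires the investigator to appraise laboratory findings and to report isolated ones that meet study criteria or need corrective treatment. Protocol 10.2.2 allows an important medical event to be an SAE on judgement. SAP 5.7 also lists grade 3 or 4 events for all phases. Protocol 10.1.1 limits these to phase 1, so that last route is not dependable, but the others exist.
- A reader might infer that the row will pair values from different visits. The wording in SAP 5.7.2 on any time after randomization governs each test separately and does not say how a two-part criterion is assembled. This is an ambiguity, and it would raise the count rather than lower it.

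**Conclusion.** The point holds as a gap in a descriptive safety definition. Under the SAP as written, a patient with AST above 3 ULN, bilirubin above 2 ULN and ALT at or below 3 ULN is never a combined case, and the separate counts cannot supply the missing number. This follows from the text of SAP 10.3 and 5.7.2 alone and needs no assumption about the cited guidance.

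The size cannot be given. The documents contain no rates for ALT, AST or bilirubin abnormalities and no share of joint events that rest on AST. Any percentage undercount would only restate an assumed share.

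The point has no bearing on the primary endpoints, the testing hierarchy, alpha or power. Serious liver events would still reach the safety tables as SAEs, and the AST and bilirubin values can still appear in their own rows. It is a cheap improvement and ranks as optional.

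**What to change.** In SAP 10.3, beside the existing combined row:

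- Add a line for ALT or AST above 3 ULN with total bilirubin above 2 ULN.
- State that the transaminase and bilirubin values come from the same sample. Apply the same rule to the ALT-only count, so that it is a true subset of the new line.
- Keep the existing baseline condition and extend it to AST: baseline of the qualifying transaminase at or below 3 ULN, or baseline total bilirubin at or below 2 ULN. Nothing is wrong with that condition, and dropping it would bring in patients already above both limits at baseline.
- Retain the ALT-only count as a sub-line, so the present criterion can still be read.

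The cost is a short SAP edit and one further derivation. No new data are needed, because AST, ALT and bilirubin come from one chemistry panel. The downside is that some AST rises of muscle origin may enter the wider count. CPK is in the same panel and can be listed beside each such case for the reader to judge.
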